7.2. Premature Termination of Treatment

The reasons for premature termination of treatment follow. Teva Branded Pharmaceutical Products R&D, Inc. should be contacted before any patient is terminated from the study.

- Intolerable adverse effects.
- Patient's voluntary decision to discontinue treatment for any reason.
- Investigator's judgment that continued treatment is not in the best interest of the patient.
- Loss of patient to follow-up.
- Pregnancy.
- Gross noncompliance (i.e., use of less than 50% of prescribed doses in the preceding 3-month period).

7.3. Concomitant Therapy

- Symptomatic agents such as anti-cholinergic and spasmolytic drugs are permitted at clinically appropriate doses.
- Short-term treatment with corticosteroids will be allowed during acute relapses.
- Medications not allowed during this trial include:
 - Other investigational drugs.
 - Other approved MS drugs
 - Interferons.
 - Immunomodulator, cytotoxic, and immunosuppressive drugs (i.e., cyclophosphamide, cyclosporine, azathioprine, etc.)

- Long term (>30 days) corticosteroids; overall dose of more than 2,000 mg oral prednisone; overall dose of more than 1,000 mg IV methylprednisolone per day for more than 7 days per treatment, with or without an appropriate tapering dose of an oral prednisone.
- All concomitant medications must be listed in the Case Report Form.

7.4. Assessment of Safety

Special attention will be given to detecting known adverse effects of Copaxone[®]. In the previous studies of Copaxone[®] in MS patients, no systemic laboratory abnormalities were observed during 2 years of dosing. Therefore, laboratory studies will be done at 6-month intervals and will consist of urinalysis, hematological evaluations, and a broad screen of blood chemistries (see Section 7.7).

Available data suggest that local reactions at the injection site have been reported more commonly in Copaxone[®]-treated than in placebo-treated patients. Soreness, itching, swelling, and redness were all reported. None of these reactions was persistent. The descriptions of such reactions will be recorded in the Case Report Form by the nurse coordinator. Appropriate observation will be continued until the patients return to baseline status.

In previous clinical studies, both Copaxone[®] and placebo-treated patients have occasionally experienced brief episodes of flushing, sweating, palpitations, a feeling of tightness in the chest, difficulty in breathing, and associated anxiety. The site should be contacted immediately and appropriate evaluation undertaken as clinically indicated. A complete description of the event should be placed in the Case Report Form.

The Medical Monitor can be consulted regarding suggested management of the above-mentioned adverse experiences.

Other adverse experiences have been reported during ongoing clinical trials with Copaxone[®]. A full accounting of adverse experiences is included in the package insert.

Any patient withdrawn from the study for drug-related side effects will be requested to continue to be observed by the physician as long as necessary until the patient's condition returns to the pre-reaction baseline.

7.5. Adverse Events

7.5.1. Definition of an Adverse Event

An adverse event is any untoward medical occurrence in a patient administered a pharmaceutical product, regardless of whether it has a causal relationship with this treatment.

In this study, any adverse event occurring after the clinical study patient has signed the informed consent form should be recorded and reported as an adverse event.

An adverse event can, therefore, be any unfavorable and unintended physical sign, symptom, or laboratory parameter that develops or worsens in severity during the course of this study, or significant worsening of the disease under study, or of any concurrent disease, whether or not considered related to the study drug. A new condition or the worsening of a pre-existing condition will be considered an adverse event. Stable chronic conditions (such as arthritis) that are present before study entry and do not worsen during this study will not be considered adverse events.

Accordingly, an adverse event can include any of the following:

- intercurrent illnesses
- physical injuries
- events possibly related to concomitant medication
- significant worsening (change in nature, severity, or frequency) of the disease under study or other pre-existing conditions
- drug interactions
- events occurring during diagnostic procedures or during any washout phase of this study
- laboratory or diagnostic test abnormalities that result in the withdrawal of the patient from the study, are associated with clinical signs and symptoms or a serious adverse event, require medical treatment or further diagnostic work-up, or are considered by the investigator to be clinically significant (Note: Abnormal laboratory test results at the screening visit that preclude a patient from entering the study or receiving study treatment are not considered adverse events.)

Hospitalization due to MS exacerbation should be recorded as an adverse event only if the presentation or outcome is more severe than would normally be expected from the normal course of the disease in a particular patient.

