7. CONDUCT OF STUDY

7.1. Schedule of Activities and Evaluations

All procedures, tests, and examinations required for the study extension visits are listed on the Schedule of Activities Flow Chart found in [Appendix A](#).

Screening visits through month 264 must have been completed to continue in the study extension. For the purposes of this amendment, the termination visit of Amendment 12 (month 264), will act as the screening visit for this amendment. Patients who have completed the termination visit and discontinued from the study under the Amendment 12 protocol may still continue in the extension study under Amendment 13; for these patients, the screening visit for Amendment 13 will be a separate visit to the termination visit of Amendment 12.

The study extension will involve 1 investigator visit (Section [7.1.3.2](#)) annually supplemented by 3 nurse coordinator telephone visits (Section [7.1.3.1](#)). This schedule will maintain contact with the patients on a quarterly basis, approximately every 90 days. The study extension period will end with the termination visit (Section [7.1.3.3](#) and Section [7.1.5](#)) following 26 years of continuous Copaxone[®] therapy.

In addition to MRIs performed at month 240, the optional MRI sub-study will involve 2 MRIs for active study patients at the annual investigator visit (month 252) or at an unscheduled visit around the time of the investigator visits and at the final investigator visit for Amendment 12/screening visit for Amendment 13 (month 264).

The optional immunological sub-study will involve 2 blood samples, 1 taken during the screening visit for Amendment 12, and 1 at the next treatment visit at month 252. There will be no additional immunological assessments under Amendment 13.

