7.1.1. Screening Visit for Amendment 13 (Month 264)

During screening for Amendment 13, the patient must be thoroughly informed about all aspects of the study extension, including the study visits and activities schedule. Written informed consent must be obtained.

At this visit, patients will be given the option of either continuing treatment with Copaxone 20 mg daily or switching to Copaxone 40 mg TIW. The choice of treatment will be recorded for each patient.

A checklist of the procedures to be performed during the screening visit follows.

- Eligibility checklist
- Signed informed consent for Amendment 13
- Record treatment (20 mg daily or 40 mg TIW)

- Complete neurological examination, including:
 - Functional Systems Status (FS) Evaluation ([Appendix D](#))
 - Kurtzke Expanded Disability Status Score (EDSS) ([Appendix C](#))
 - AI ([Appendix E](#))
- Complete physical examination
- Laboratory studies as outlined in Section [7.7](#)
 - Urinalysis
 - Hematology
 - Serum chemistries
- Adverse experiences
- Evidence of relapse
- Concomitant therapy
- Drug accountability

The visit procedures listed above may be completed as an unscheduled visit if the month 264 visit has already been completed.

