7.1.2. Treatment Initiation

A patient found eligible for the study extension will continue Copaxone[®] therapy. Patients will be instructed again in preparation and self-administration of Copaxone[®]. Patients will be given all necessary supplies and a detailed instruction sheet, which will be reviewed with the patient at the visit. In addition, patients will be instructed to contact the study center if questions or problems arise.

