7.5.5. Serious Adverse Events

7.5.5.1. Definition of a Serious Adverse Event

A serious adverse event is an adverse event occurring at any dose that results in any of the following outcomes or actions:

- death
- a life-threatening adverse event (ie, the patient was at immediate risk of death from the event as it occurred); does not include an event that, had it occurred in a more severe form, might have caused death
- inpatient hospitalization or prolongation of existing hospitalization, which means that hospital inpatient admission or prolongation of hospital stay were required for treatment of an adverse event, or that they occurred as a consequence of the event

Hospitalizations scheduled before the patient signed the informed consent form will not be considered serious adverse events, unless there was worsening of the preexisting condition during the patient's participation in this study.

- Hospitalization for intravenous steroid treatment of a relapse will not be considered a serious adverse event unless it is a worsening of the condition beyond expected disease progression.
- persistent or significant disability or incapacity (refers to a substantial disruption of one's ability to conduct normal life functions)
- a congenital anomaly/birth defect
- an important medical event that may not result in death, be life-threatening, or require hospitalization, but may jeopardize the patient and may require medical intervention to prevent one of the outcomes listed in this definition
- Examples of such events are intensive treatment in an emergency room or at home for allergic bronchospasm; blood dyscrasias or convulsions that do not result in hospitalization; or the development of drug dependency or drug abuse. Note: Any suspected transmission of an infectious agent via a medicinal product is considered an important medical event.

All occurrences of possible drug-induced liver injury that meet Hy's law criteria, defined as **all** of the below, must be reported by the investigator to the sponsor as a serious adverse event:

- alanine aminotransferase (ALT) or aspartate aminotransferase (AST) elevation of >3x the upper limit of normal (ULN)
- total bilirubin elevation of >2x ULN
- absence of initial findings of cholestasis (ie, no substantial increase of alkaline phosphatase [ALP])

An adverse event that does not meet any of the criteria for seriousness listed above will be regarded as a nonserious adverse event.

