7.8. Laboratory Procedures

Blood samples and urine specimens must be obtained at the appropriate visits. Non-fasting samples may be obtained. Any laboratory samples which are outside the normal range must be assigned one of the following codes:

NS – Not Clinically Significant: A clinically meaningless departure from the normal range.

LE – Laboratory Error: Due to a poor sample, instrument error, etc. (the value is not valid).

PA – Patient Abnormality: Although the value is outside the normal range, the value is normal for that particular patient.

CS – Clinically Significant: A clinically meaningful departure from the normal range or a clinically meaningful change in the parameter. All clinically significant values during the study are adverse events and must be entered on the “Clinically Significant Lab Values” page of the Case Report Form.

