APPENDIX A. SCHEDULE OF ACTIVITIES AND EVALUATIONS

Procedures Performed	Study Visit				
	Screening Visit for Amendment 13 (Month 264) ^a	Unscheduled Visits as necessary for Protocol	Nurse Coordinator Telephone Visits ^b	Investigator Visits (Month 276)	Termination Visit (scheduled Month 288)
Study Extension Informed Consent	X				
Visit Checklist	X	X	X	X	X
Evidence of Relapse	X	X ^c	X	X	X
Physical Examination	X	X ^c			X
Urinalysis	X	X ^c		X	X
Hematology	X	X ^c		X	X
Serum Chemistries	X ^d	X ^{c,d}		X	X
Serum/Pregnancy Test (where appropriate)		X ^c			X ^e
Adverse Experiences	X	X ^c	X	X	X
Concomitant Therapy	X	X ^c	X	X	X
Medication History		X ^c			
Record Treatment	X			X	
Drug Accountability	X	X ^c	X	X	X
Neurological Assessments	X	X ^c		X	X
Termination Reason					X ^e
Optional MRI	X	X ^c			

^a This will be the same visit as the termination visit for Amendment 12, except for patients who completed the termination visit of Amendment 12 but were not able to immediately enter Amendment 13; for these patients, the Amendment 13 visit will be distinct from the Amendment 12 termination visit.

^b Months 267, 270, 273, 279, 282, and 285

^c Optional as deemed necessary for the visit

^d Serum creatinine should be obtained prior to an MRI scan

^e For early termination only.

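### The screening-laboratory exemption in 7.5.1 lands on month 264, an on-treatment visit for most patients, and contradicts other adverse-event rules with no stated precedence

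*Combined protocol and SAP*

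**What the plan says.** The bullet in 7.5.1 on laboratory abnormalities makes them adverse events when they lead to withdrawal, come with symptoms or a serious event, need treatment or work-up, or are judged clinically significant. The Note that closes the bullet takes some results back out: abnormal "laboratory test results at the screening visit that preclude a patient from entering the study or receiving study treatment are not considered adverse events".

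Section 7.1 fixes which visit that is: "the termination visit of Amendment 12 (month 264), will act as the screening visit for this amendment". Footnote a of Appendix A agrees: "This will be the same visit as the termination visit for Amendment 12, except for patients who completed" the Amendment 12 termination visit but could not enter Amendment 13 at once. Section 7.1.1 lists urinalysis, hematology and serum chemistries at this visit. Section 7.1.2 describes continuation of therapy, not a start: "A patient found eligible for the study extension will continue Copaxone".

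Section 7.8 states, without a screening exception, "All clinically significant values during the study are adverse events". Appendix F requires every adverse laboratory to be recorded. Section 7.5.5.1 requires every case meeting Hy's law criteria to be reported as serious.

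Section 7.5.5.1 also has an exemption tied to consent: "Hospitalizations scheduled before the patient signed the informed consent form will not be considered serious adverse events", unless the condition worsened during participation.

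**The concern.** An exemption for screening laboratory results presumes a patient who has not yet taken study drug, so that the abnormality cannot reflect exposure. In this extension most patients reach screening after many years on Copaxone. A blood count or liver result at month 264 that leads the investigator not to carry the patient forward is an on-treatment finding, and the Note lets it be classed as no adverse event.

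Long-term safety is the first objective in Section 3. Under Section 8.1, the incidence tables, and the narratives for patients who withdrew because of an adverse event, depend on adverse-event status. If sites resolve the conflict differently, identical results will be coded differently. Applying the Note can only remove events from these displays; it cannot add any.

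**Working it through.** The documents state no figure to reproduce, so the check is mainly a comparison of rules.

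**1. Is month 264 on treatment?** On the study clock, 264/12 = 22 years. Section 4 associates month 264 with 24 years of continuous therapy. The difference of 2 years is consistent with adding the 24-month planned double-blind period. With the continuation wording in 7.1.2, this supports reading month 264 as on treatment for patients who move straight from Amendment 12 to Amendment 13. Patients who completed and discontinued under Amendment 12 have a separate later screening visit (7.1) and may be off drug then.

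**2. One on-treatment month 264 result, clinically significant, after which the patient is not carried forward:**

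| Rule | Classification |
|---|---|
| 7.5.1, body of the laboratory bullet | Adverse event (clinically significant; arguably also a withdrawal) |
| 7.5.1, Note | Not an adverse event |
| 7.8 | Adverse event, entered on the dedicated CRF page |
| Appendix F | Adverse laboratory, must be recorded |
| 7.5.5.1, if Hy's law criteria are met | Reported as a serious adverse event |

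No text ranks these rules. The Note is the specific exception inside the general bullet, so a site could reasonably let it govern. Section 7.8 is unqualified, so another site could reasonably do the opposite.

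**3. How could a laboratory value bar entry?** Sections 6.1 and 6.2 contain no laboratory threshold. The route is the investigator's judgment of physical stability in 6.1. That limits how often the Note can apply.

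**4. Which outputs are exposed?** The adverse-event tables and the adverse-event withdrawal narratives (8.1). The laboratory summaries in 8.2 do not depend on adverse-event coding.

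**5. Scale only.** Month 264 is one of three scheduled laboratory draws in this extension (264, 276, 288). Section 3 gives approximately 60 patients. Taking n = 60 as an assumed denominator:

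- One omitted case: 1/60 = 1.67 percentage points.
- Exact (Clopper-Pearson) 95% intervals: 0/60 = 0% (0 to 5.96%); 1/60 = 1.67% (0.04 to 8.94%).
- The per-patient probability p of such a result at month 264 is not in the documents. Assuming independent patients, the chance of at least one case is 1 − (1 − p)^60:

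| Assumed p | Expected cases (60p) | Chance of at least one |
|---|---|---|
| 0.5% | 0.3 | 26% |
| 1% | 0.6 | 45% |
| 2% | 1.2 | 70% |
| 5% | 3.0 | 95% |

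**6. Which consent and which entry date?** Section 7.5.2 starts adverse-event recording at signature of the consent form. Section 7.5.5.1 ties the planned-hospitalization exemption to a consent signature, and 7.5.1 excludes stable chronic conditions that predate study entry. Sections 6.1 and 7.1.1 require a new consent for Amendment 13. None of the safety definitions says whether the original or the new consent, or the original or the extension entry, is meant.

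**The case against.** The strongest reply is that the result is captured anyway. The body of the same bullet, 7.8, Appendix F and, where it applies, the Hy's law rule all classify or record it. For a patient already on drug, stopping because of a laboratory value reads naturally as withdrawal, which the bullet makes an adverse event. This defeats the stronger reading a reader might take from the Note, that such a result is settled as a non-event and the safety profile is therefore biased. The documents do not say that the Note prevails. The reply does not remove the conflict, however: a patient who completes month 264 and is not carried forward can also be described as not having entered, and the rules are left unranked.

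Several limits also stand. With no laboratory eligibility threshold, cases are probably few. The Note may fit patients who are off drug at a separate screening visit. The values are not lost, because 8.2 summarizes them. The figure of about 60 is not stated to be the number screened at month 264, nor to be the all-patients-treated denominator of 8.1.

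A reader might also infer from 7.5.5.1 that admissions for disease arising on drug become exempt if booked just before the Amendment 13 consent, for example surgery for a tumour. The documents do not support that. Appendix F lists cancer as serious in its own right, 7.5.5.1 restores seriousness when the condition worsens during participation, and the text does not say that the Amendment 13 consent is the one meant. What remains of this is an undefined date.

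**Conclusion.** The point holds as an unresolved contradiction. A Note written for patients not yet on drug is attached to a visit at which most patients are on drug, and it conflicts with at least three other current rules (the rest of its bullet, 7.8 and Appendix F), and with a fourth when Hy's law criteria are met. A site applying it would omit an on-treatment abnormality that ended participation from the adverse-event tables and withdrawal narratives, but not necessarily from the laboratory summaries.

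The size cannot be estimated from the documents. It is probably small in number of cases: each would be 1.7 points if the denominator is 60, and the probabilities shown rest on assumed rates. A claim that the safety results are biased is not supported. The undefined consent and study-entry dates are a secondary matter of clarity.

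**What to change.** - In 7.5.1, delete the Note, or limit it to patients who are off study drug at a separate Amendment 13 screening visit.
- State that month 264 results obtained on treatment follow 7.8 and Appendix F, whether or not the patient enters Amendment 13.
- In 7.5.1, 7.5.2 and 7.5.5.1, say which consent and which study-entry date are meant, preferably the original study consent and entry, not the Amendment 13 re-consent.

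The cost is a few edited sentences in an amendment, with no added visits, tests or patients. The downside is that a few more adverse events may be reported.

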7.5.2. Recording and Reporting of Adverse Events

For recording of adverse events, the study period is defined for each patient as that time period from signature on the informed consent form until the last study visit.

All adverse events that occur during the defined study period must be recorded on the source documentation and transcribed to the CRF, regardless of the severity of the event or judged relationship to the study drug. For serious adverse events, the serious adverse event form must be completed and the serious adverse event must be reported immediately (see Section 7.5.5.3). The investigator does not need to actively monitor patients for adverse events once the study has ended. Serious adverse events occurring in a patient after the treatment of that patient has ended

should be reported to the sponsor if the investigator becomes aware of them, following the procedures described in see Section 7.5.5.3.

At each contact with the patient, the investigator or designee must question the patient about adverse events by asking an open-ended question such as “Have you had any unusual symptoms or medical problems since the last visit? If yes, please describe”. All reported or observed signs and symptoms will be recorded individually, except when considered manifestations of a medical condition or disease state. A precise diagnosis will be recorded whenever possible. When such a diagnosis is made, all related signs, symptoms, and any test findings will be recorded collectively as a single diagnosis on the CRF and, if it is a serious adverse event, on the serious adverse event form.

The clinical course of each adverse event will be monitored at suitable intervals until resolved, stabilized, or returned to baseline; or until the patient is referred for continued care to a health care professional; or until a determination of a cause unrelated to the study drug or study procedure is made.

The onset and end dates, duration (in case of adverse event duration of less than 24 hours), action taken regarding study drug, treatment administered, and outcome for each adverse event must be recorded on the source documentation and transcribed to the CRF.

The relationship of each adverse event to study drug and study procedures, and the severity and seriousness of each adverse event, as judged by the investigator, must be recorded as described below.

